#### **5.3.4. Safety Monitoring and Study Drug Interruption/Dose Modification**

Subjects must be monitored closely for adverse events or laboratory abnormalities during the course of the study. Reference should be made to the CTCAE, Version 4.03 for grading the severity of adverse events and laboratory abnormalities.

Recommendations and requirements for modifications of the dosing regimens based on the drug agent as well as the type and severity of adverse events or laboratory abnormalities are provided in [Table 5-4](#) below. The dose modification instructions focus on the types of events most commonly attributed to each of the study agents. Required dose modifications and actions (in bold and italic) provided in [Table 5-4](#) must be followed based on the type and severity of adverse event. The recommendations provided in [Table 5-4](#) (not italicized) comprise only guidelines; variations from these recommendations may be warranted based on an investigator's individual judgment in considering potential risks, benefits, and therapeutic alternatives available to each subject.

Consistent with [Table 5-4](#), if a subject experiences an adverse event that is suspected to be related to idelalisib during the course of study, then study drug administration should be held, as outlined in [Table 5-4](#), until the adverse event resolves or stabilizes to an acceptable degree (requirements vs recommendations defined in [Table 5-4](#)). Thereafter, study drug may be reinstated at either the starting dose level (150 mg BID) or at Dose Level-1 (100 mg BID) consistent with the instructions in [Table 5-4](#). One further attempt at reinitiation of therapy at Dose Level -1 (100 mg BID) may be attempted if the investigator feels that a second rechallenge at that dose level is medically appropriate. If the subject cannot tolerate study drug at 100 mg BID after 2 rechallenges, then the subject should be discontinued from study drug therapy unless continued therapy is permitted by the Gilead Sciences medical monitor.

After a study drug dose reduction, the dose need not be re-escalated, even if there is minimal or no toxicity with the reduced dose. However, if the subject tolerates the lower dose level of study drug for  $\geq 4$  weeks then the dose may be increased to 150 mg BID, at the discretion of the investigator. Such re-escalation may be particularly warranted if further evaluation reveals that the adverse event that led to the dose reduction was not study-drug-related. The starting dose level should not intentionally be exceeded in this study.

Escalations or reductions in ofatumumab dosing are not planned. As noted in [Table 5-4](#), ofatumumab administrations may be delayed to allow subjects to recover from ofatumumab-related adverse events or intercurrent illness.

Whenever possible, any dose adjustment of idelalisib should be discussed between the investigator and the Gilead Sciences medical monitor prior to implementation. To implement either a dose reduction or a dose reescalation, the investigator/study staff member will access the IWRS, select the subject number, and inform the IWRS of the need for dose titration. The IWRS will provide details regarding the kit numbers to be dispensed to the subject. The appropriate clinic staff should instruct the subject/caregiver about the change in dose.

**Table 5-4. Recommendations and *Required* Actions for Idelalisib and Ofatumumab Dose Modification Based on Type and Severity of Treatment-Related Adverse Event or Laboratory Abnormality**

NCI CTCAE Grade	Recommendations and Required Action (in italics)	
	Idelalisib	Ofatumumab
HEMATOLOGICAL ADVERSE EVENTS		
Neutropenia		
Grade $\leq 2$ neutropenia	Maintain current dose level and schedule.	Maintain current dose level and schedule.
Grade $\leq 3$ neutropenia	Maintain current dose level and schedule. Blood counts must be monitored at least weekly until ANC <math>\leq</math> Grade 2.	Maintain current dose level and schedule. Consider G-CSF support.
Grade 4 neutropenia (or occurrence of neutropenic fever or infection)	Interrupt idelalisib. Blood counts must be monitored at least weekly until ANC <math>\leq</math> Grade 2, at which point idelalisib dosing may be resumed at lower dose level.	Delay ofatumumab until Grade $\leq 3$ (ANC $\geq 0.5 \times 10^9/L$ ) and/or neutropenic fever or infection is resolved; thereafter, resume at full dose. Consider G-CSF support to avoid delays. If delay is $> 4$ weeks, discontinue ofatumumab.
Thrombocytopenia		
Grade $\leq 3$	Maintain current dose level and schedule.	Maintain current dose level and schedule.
Grade 4	During combination therapy period, maintain current idelalisib dose level. During continuing therapy period, withhold idelalisib for bruising or bleeding until Grade <math>\leq 3</math>. May resume idelalisib at same or reduced dose level at investigator discretion.	Delay ofatumumab until Grade $\leq 3$ (platelets $\geq 25 \times 10^9/L$ ); thereafter, resume at full dose. If delay is $> 4$ weeks, discontinue ofatumumab.
NON-HEMATOLOGICAL ADVERSE EVENTS		
Cutaneous		
Grade $\leq 1$	Maintain current dose level and schedule.	Maintain current dose level and schedule.
Grade 2	Maintain current dose level and schedule.	Delay ofatumumab until Grade $\leq 1$ ; thereafter, resume at full dose.

NCI CTCAE Grade	Recommendations and Required Action (in italics)	
	Idelalisib	Ofatumumab
Grade 3 or 4	Withhold idelalisib until Grade ≤ 1. May resume at lower dose level or discontinue idelalisib at investigator discretion.	Delay ofatumumab until Grade ≤ 1; thereafter, may resume at full dose or discontinue ofatumumab at investigator discretion.
Stevens-Johnson Syndrome/Toxic Epidermal Necrolysis		
Any Grade	Discontinue idelalisib. Interrupt coadministered medications potentially associated with SJS or TEN. Institute treatment per institutional standards.	
Gastrointestinal Inflammation/Diarrhea		
Grade ≤1	Provide anti-diarrheal agent (eg, loperamide) and maintain current idelalisib dose level and schedule. Obtain history and perform physical exam as outlined in Section 5.4.3.2	Maintain current dose level and schedule.
Grade 2	Provide anti-diarrheal (eg, loperamide). Consider addition of anti-inflammatory agent (eg, sulfasalazine, budesonide). Maintain current study drug dose and schedule. Obtain stool culture, history, and perform physical exam as outlined in Section 5.4.3.2	Maintain current dose level and schedule.
Grade 3	Withhold idelalisib. Rule out infectious etiology including CMV. Consider anti-diarrheal agent (eg, loperamide) and/or addition of anti-inflammatory agent (eg, sulfasalazine, budesonide). Obtain stool culture, history, and perform physical exam as outlined in Section 5.4.3.2. Perform endoscopy with biopsy as outlined in Section 5.4.3.2. At Grade ≤1, may resume at lower dose level or discontinue study drug at investigator discretion.	Delay ofatumumab as necessary to ensure subject is sufficiently stable to receive further treatment; thereafter maintain full dose and schedule.
Grade 4	Withhold idelalisib. Rule out infectious etiology including CMV. Consider anti-diarrheal agent (eg, loperamide) and/or addition of anti-inflammatory agent (eg, sulfasalazine, budesonide). Obtain stool culture, history, and perform physical exam as outlined in Section 5.4.3.2. Perform endoscopy with biopsy as outlined in Section 5.4.3.2. At Grade ≤1, may resume at lower dose level or discontinue study drug at investigator discretion.	Delay ofatumumab as necessary to ensure subject is sufficiently stable to receive further treatment; thereafter maintain full dose and schedule.

NCI CTCAE Grade	Recommendations and Required Action (in italics)	
	Idelalisib	Ofatumumab
Hepatic Adverse Events (elevations in ALT, AST, or bilirubin)		
Grade ≤1 (ALT/AST≤3xULN) (Bilirubin≤1.5xULN)	Maintain current dose level and schedule.	Maintain current dose level and schedule.
Grade 2 (ALT/AST>3-5xULN) (Bilirubin>1.5- ≤3xULN)	Maintain current dose level and schedule. Monitor ALT, AST, ALP, and bilirubin at least 1x per week until all abnormalities are Grade <1.	Maintain current dose level and schedule.
Grade 3 (ALT/AST>5-20xULN) (Bilirubin>3-10xULN)	Withhold idelalisib. Monitor ALT, AST, ALP, and bilirubin at least 1x per week until all abnormalities are Grade ≤ 1. If bilirubin abnormality was Grade < 3, resume idelalisib at same dose level. If bilirubin abnormality was Grade ≥ 3, resume idelalisib at lower dose level.	Delay ofatumumab as necessary to ensure subject is sufficiently stable to receive further treatment; thereafter maintain full dose and schedule.
Grade 4 (ALT/AST>20xULN) (Bilirubin>10xULN)	Withhold idelalisib. Monitor ALT, AST, ALP, and bilirubin at least 1x per week until all abnormalities are Grade ≤ 1. If bilirubin abnormality was Grade < 4, resume idelalisib at lower dose level. If bilirubin abnormality was Grade 4, discontinue idelalisib.	Delay ofatumumab as necessary to ensure subject is sufficiently stable to receive further treatment; thereafter maintain full dose and schedule.
Pneumonitis (with new onset or worsening of baseline, dyspnea, cough, or hypoxia without obvious infectious cause)		
Grade 1 (asymptomatic)	Withhold idelalisib until resolution to baseline. May resume at lower dose level or discontinue study drug at investigator discretion.	Maintain current dose level and schedule.
Grade ≥ 2	Discontinue idelalisib permanently in subjects with any severity of symptomatic pneumonitis and institute therapy as clinically appropriate.	Delay ofatumumab as necessary to ensure subject is sufficiently stable to receive further treatment; thereafter maintain full dose and schedule.
Other Nonhematological Adverse Events		
Grade ≤ 2	Maintain current dose level and schedule	Maintain current dose level and schedule.
Grade ≥ 3	Withhold idelalisib until Grade ≤ 1. May resume idelalisib at initial or lower dose level or discontinue idelalisib at investigator discretion.	Delay ofatumumab as necessary to ensure subject is sufficiently stable to receive further treatment; thereafter maintain full dose and schedule or discontinue ofatumumab at investigator discretion.
Pneumocystis jirovecii pneumonia (PJP)		
Any Grade	Discontinue idelalisib permanently	

NCI CTCAE Grade	Recommendations and Required Action (in italics)	
	Idelalisib	Ofatumumab
Organizing Pneumonia		
Any Grade	Discontinue idelalisib permanently	
CMV infection/reactivation		
Any Grade	Interrupt idelalisib upon unequivocal clinical or laboratory evidence of CMV infection.            Provide treatment according to established clinical guidelines.            If the benefits of resuming idelalisib are judged to outweigh the risks, consideration should be given to administering pre-emptive CMV therapy.	

**Abbreviations:** ALP=alkaline phosphatase, ALT=alanine aminotransferase, AST= aspartate aminotransferase, ANC=absolute neutrophil count, CTCAE=Common Terminology Criteria for Adverse Events, G-CSF=granulocyte colony-stimulating factor, NCI=National Cancer Institute, ULN=upper limit of normal, CMV=Cytomegalovirus

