#### 5.4.4. Hematological and Immunological Events

In the Phase 1 experience with idelalisib in CLL, patients with Grade  $\geq 3$  neutropenia, anemia, and/or thrombocytopenia were enrolled to clinical trials. Decreased levels of neutrophil counts, hemoglobin, or platelet counts during therapy were largely due to minor fluctuations in these parameters among patients with pre-existing hematological abnormalities due to disease or prior therapy. Thus, idelalisib did not appear to induce overt myelosuppression. Obvious patterns of drug-mediated reductions in circulating CD4+ lymphocyte counts or suppression of serum IgG levels were also not observed.

Treatment-emergent Grade 3 or 4 neutropenia events, including febrile neutropenia, have occurred in subjects treated with idelalisib. All subjects should have their blood counts monitored at least every 2 weeks for the first 6 months of idelalisib treatment. For subjects who develop ANC 0.5 to  $< 1.0$  Gi/L, blood counts must be monitored weekly. For subjects who develop ANC  $< 0.5$  Gi/L, idelalisib must be interrupted and blood counts monitored weekly until ANC is  $\geq 0.5$  Gi/L, at which point, idelalisib dosing may be resumed at 100 mg BID. Neutropenia should be managed according to established clinical guidelines.

Prolonged ( $\geq 1$  week) severe neutropenia can occur with ofatumumab. Of 108 patients with normal neutrophil counts at baseline in the Phase 2 pivotal clinical trial experience {Wierda 2010}, 45 (42%) developed Grade  $\geq 3$  neutropenia and 19 (18%) developed Grade 4 neutropenia. Some patients experienced new onset Grade 4 neutropenia of  $> 2$  weeks in duration {Glaxo Group Limited 2011}. Suppression of mean serum IgG and IgA levels has not been seen. Anemia and thrombocytopenia are not as prominent.

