Because idelalisib is not associated with substantial myelotoxicity, alterations in idelalisib therapy for such events during combination idelalisib/ofatumumab therapy should be avoided, if possible. Dose modifications during combination idelalisib/ofatumumab therapy (Arm A) or during single-agent ofatumumab therapy (Arm B) should focus on alterations in ofatumumab scheduling; in subjects with persistent neutropenia despite G-CSF administration, ofatumumab doses may be delayed for as long as 4 weeks to allow recovery of neutrophil counts to Grade  $\leq 3$  (see Table 5-4). At the conclusion of combination therapy, subjects with protracted or symptomatic neutropenia or thrombocytopenia during continuing single-agent idelalisib therapy may warrant a study drug dose modification if myelosuppression is unresponsive to G-CSF supportive care or is symptomatic. No modification of either drug for changes in circulating CD4+ counts or Ig levels is planned.

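### Table 5-4 and Section 5.4.4 set different neutrophil conditions for restarting idelalisib after Grade 4 neutropenia, and Section 5.4.4 also pulls against the mandatory interruption

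*Protocol*

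**What the plan says.** **Protocol Section 5.3.4, Table 5-4, Grade 4 neutropenia row, idelalisib cell.** The text is in bold italics, which Section 5.3.4 defines as a required action. Idelalisib is interrupted and counts are taken at least weekly until the ANC is no worse than "Grade 2, at which point idelalisib dosing may be resumed at lower dose level". The row also covers neutropenic fever or infection.

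**Same row, ofatumumab cell.** Ofatumumab is delayed until Grade 3 or better, which the cell writes as ANC of at least 0.5 × 10⁹/L, "and/or neutropenic fever or infection is resolved; thereafter, resume at full dose".

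**Protocol Section 5.4.4, treatment-emergent neutropenia paragraph.** At ANC 0.5 to below 1.0 "Gi/L, blood counts must be monitored weekly". Below 0.5 Gi/L, "idelalisib must be interrupted and blood counts monitored weekly until ANC is" at least 0.5 Gi/L, "at which point, idelalisib dosing may be resumed at 100 mg BID".

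**Protocol Section 5.4.4, final paragraph.** Because idelalisib is described as not substantially myelotoxic, "alterations in idelalisib therapy for such events during combination idelalisib/ofatumumab therapy should be avoided, if possible", and dose changes are to centre on the ofatumumab schedule. In the later single-agent period, protracted or symptomatic neutropenia or thrombocytopenia "may warrant a study drug dose modification if myelosuppression is unresponsive to G-CSF supportive care or is symptomatic".

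**Table 5-4, Grade 4 thrombocytopenia row.** This row does separate the treatment periods: "During combination therapy period, maintain current idelalisib dose level", with a different, required instruction for the continuing-therapy period.

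**The concern.** Two passages in the same chapter govern the same event and lead to the same restart dose, but they release the hold at different neutrophil counts. A site working from Section 5.4.4 may restart idelalisib while a required action in Table 5-4 still holds it. A site working from the last paragraph of Section 5.4.4 may treat a mandatory interruption as discretionary during combination therapy.

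The rule is likely to be used. The protocol reports Grade 3 or worse neutropenia in 46 of 191 subjects (24%) in the Phase 1 idelalisib monotherapy study. It reports Grade 4 neutropenia in 19 of 108 ofatumumab patients (18%) with normal baseline counts in the pivotal Phase 2 trial. Subjects with any degree of baseline neutropenia may enroll. With about 115 planned centers, sites that read the text differently would manage the same count differently, and it would be unclear what counts as a protocol deviation.

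**Working it through.** No sample size, power or error rate is involved. The check sets the passages side by side on one scale; Gi/L and 10⁹/L are the same unit.

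1. **Trigger.** Table 5-4 uses Grade 4; Section 5.4.4 uses ANC below 0.5 Gi/L. The ofatumumab cell equates Grade 3 or better with ANC of at least 0.5 × 10⁹/L, so Grade 4 is below 0.5 and the count triggers agree. Only the table adds neutropenic fever or infection.

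2. **Restart dose.** Table 5-4 says the lower dose level; Section 5.4.4 says 100 mg BID. Table 5-2 has one lower level, 100 mg BID. These agree.

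3. **Restart count.** Table 5-4 requires Grade 2 or better. Section 5.4.4 requires ANC of at least 0.5 Gi/L, which is Grade 3 or better on the protocol's own mapping. These differ by one grade. The protocol grades by CTCAE 4.03 but does not print the ANC cut-off between Grades 2 and 3. If the weekly-count rule in the Table 5-4 row above and the one in Section 5.4.4 describe the same band (an assumption), the disputed band is ANC 0.5 to below 1.0 Gi/L.

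4. **Interruption by period.** The Grade 4 neutropenia row and the Section 5.4.4 neutropenia paragraph require interruption with no split by period. The last paragraph of Section 5.4.4 asks sites to avoid idelalisib changes where possible during combination therapy and speaks permissively about the later period. The thrombocytopenia row shows that the protocol can separate the periods when it intends to.

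5. **Weekly counts.** The stated end points are Grade 2 or better (Table 5-4) and ANC of at least 0.5 Gi/L (Section 5.4.4). Section 5.4.4 separately requires weekly counts at 0.5 to below 1.0 Gi/L, so the practical difference is small.

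6. **Secondary: count frequency.** Section 5.4.4 asks for counts at least every 2 weeks for the first 6 months of idelalisib; Appendix 7 and the synopsis schedule fewer. Assume a start on Day 1 and 6 months = 183 days, ending on Day 184.
   - Two-weekly dates after Day 50: 64, 78, 92, 106, 120, 134, 148, 162, 176 = 9.
   - Scheduled in Appendix 7: 78, 106, 134, 162 = 4. Shortfall: 9 − 4 = 5.
   - Longest gaps with the ±3-day windows: 28 + 3 + 3 = 34 days between 4-weekly visits; 42 + 3 + 3 = 48 days from Day 162 to Day 204.
   - Part of that last gap inside the 6 months: 184 − 162 = 22 days, or 184 − 159 = 25 days if the Day 162 visit is 3 days early.

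   Unscheduled counts are allowed, so both texts can be followed. This is not a contradiction.

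**The case against.** The strongest reply is that precedence is largely settled. Section 5.3.4 says the required actions in Table 5-4 must be followed and ties reinstatement to that table. Section 5.4 is headed as recommendations, Section 5.4.4 itself refers to Table 5-4, and Section 8.5 sends readers to Section 5.3.4 for dose modification. The restart sentence in Section 5.4.4 is permissive, so a site that waits for Grade 2 or better breaches neither text.

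Most of this is correct, and it favours the table. It does not withdraw the restart permission in Section 5.4.4, which sits in a paragraph that itself uses *must* for interruption and weekly counts, and no clause says which text prevails. That one course satisfies both texts helps only a site that has noticed both.

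On the last paragraph of Section 5.4.4, the objection is that a soft preference yields to a specific mandatory rule, and that the neutropenia and thrombocytopenia rows may properly differ. That stands in part: this is a tension, not a flat contradiction. It is still real, because the paragraph plainly covers neutropenia and makes no exception for the Grade 4 case.

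The weekly-count difference is minor, and the two-weekly frequency is a matter of alignment only. Discussion with the medical monitor whenever possible and the IWRS step for a dose reduction lower the risk, but neither states which condition applies.

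**Conclusion.** The concern holds and should be fixed. The restart conditions in Table 5-4 and Section 5.4.4 differ by one grade on the protocol's own mapping of grade to count. That conclusion needs no outside figure; only the numerical band (0.5 to below 1.0 Gi/L) rests on the assumption in step 3. The passage on avoiding idelalisib changes during combination therapy pulls against the mandatory interruption and should be settled at the same time. The weekly-count end point and the two-weekly frequency are lesser points. The consequence is for subject safety and uniform conduct; no effect on the primary endpoint or Type I error is claimed. No view is taken on which threshold or clinical rule is right.

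**What to change.** Reconcile the neutropenia rows of Table 5-4 with both paragraphs of Section 5.4.4 so that three things read the same throughout:

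- one neutrophil condition for restarting idelalisib;
- one end point for the weekly counts;
- one statement on whether interruption is mandatory in each treatment period.

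Add a clause saying which text prevails if Section 5.3.4 and Section 5.4 differ. The sponsor's clinical team chooses the values. As a secondary step, make the count frequency in Section 5.4.4 agree with Appendix 7 and the synopsis, in whichever direction the sponsor decides.

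The core change costs a protocol clarification letter or amendment wording. If the two-weekly text is kept and scheduled, it means about 5 more counts per Arm A subject than Appendix 7 shows: 5 × 170 = 850, or 5 × 180 = 900 if 270 are enrolled (270 × 2/3 = 180). These totals are upper figures, because they assume every Arm A subject stays on idelalisib for 6 months, and Section 5.4.4 already asks for the counts.

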## 5.4. Recommendations for Evaluation, Intervention, and Drug Discontinuation for Specific Adverse Events or Conditions

### 5.4.1. Carcinogenesis and Mutagenesis

Idelalisib was not genotoxic in a standard battery of assays. No carcinogenicity or mutagenicity studies of ofatumumab have been conducted. In a repeat-dose toxicity study, no tumorigenic or unexpected mitogenic responses were noted in cynomolgus monkeys treated for 7 months with up to 3.5 times the human dose of ofatumumab. Patients receiving therapies such as idelalisib or ofatumumab for CLL or iNHL have developed more aggressive lymphoid malignancies (eg, experienced Richter transformation) {[Coutre 2011](#), [Kahl 2011](#), [Wierda 2010](#)}. The specific association of the therapeutic agents with these types of events has not been determined.

Subjects who develop Richter transformation or acute myeloid leukemia should have study drug (idelalisib and ofatumumab) discontinued. For the new diagnosis of other types of disorders (eg, myelodysplastic syndrome, myeloproliferative disorders, a solid tumor), study drug (idelalisib and/or ofatumumab) may be continued at the investigator’s discretion considering benefit:risk relating to therapy, CLL, and the new dysplastic or neoplastic condition.

### 5.4.2. Dermatological Events

Subjects receiving idelalisib with  $\geq$  Grade 3 rash have generally presented with a maculopapular rash on the trunk and extremities that is occasionally associated with fever and/or pruritus and responded to treatment with diphenhydramine and/or topical or oral corticosteroids.

For subjects who develop a severe rash for which an underlying etiology cannot be identified (e.g., infection, co-suspect drug), study drug *must* be interrupted. Once rash resolves to Grade <1 idelalisib can be resumed at a lower dose level or discontinued at the investigator’s discretion.

Severe cutaneous reactions, including fatal events of Stevens-Johnson syndrome (SJS) and toxic epidermal necrolysis (TEN), have been reported in subjects receiving idelalisib. Assessment of potential causal association between idelalisib and the occurrence of SJS or TEN

has been confounded by the coadministration of antineoplastic agents (e.g., bendamustine, rituximab) and/or other concomitant medications known to be associated with SJS or TEN (e.g., allopurinol). If SJS or TEN is suspected, idelalisib and all coadministered medications associated with SJS or TEN should be interrupted and the subject treated accordingly.

Subjects should be monitored for the development of SJS, TEN, or other severe cutaneous reactions and idelalisib treatment **must** be discontinued if such events occur.

Severe dermatological reactions can occur in patients receiving ofatumumab, most commonly as manifestations of an infusion reaction. Dermatological adverse events have included macular rash, vesicular rash, urticaria, and hyperhidrosis {[Glaxo Group Limited 2011](#)}.

In the case of the occurrence of mucocutaneous reactions during ofatumumab infusion, the recommendations for the management of infusion toxicity (see Section 5.3.3.3) should be followed. The safety of readministration of ofatumumab to patients with other types of severe mucocutaneous reactions has not been determined; thus, for subjects experiencing a Grade  $\geq 3$  non-infusion-related ofatumumab mucocutaneous reaction, consideration should be given to discontinuation of ofatumumab.

